**Table summarizing results for power in detecting differential abundance:**

		Taxa Abundance	Group Sizes			
			20vs100	40vs100	50vs100	75vs100
Relative difference	50%	0.25-1.0%	20.5%	30.6%	34.2%	40.6%
		>1.0%	40.0%	54.9%	59.3%	66.4%
	100%	0.25-1.0%	52.7%	67.2%	71.0%	76.5%
		>1.0%	77.7%	88.8%	91.2%	94.5%
	200%	0.25-1.0%	84.6%	92.3%	93.9%	96.0%
		>1.0%	97.9%	99.6%	99.8%	99.9%
	300%	0.25-1.0%	95.0%	98.2%	98.7%	99.3%
		>1.0%	99.9%	100.0%	100.0%	100.0%

#### 4.3 Procedures/Methods.

##### **Subject recruitment and enrollment:**

Subjects for this study will be between the ages of 18 and 79 with a colon cancer diagnosis, and will be recruited from one of two participating sites (Waco, Temple). We plan to include at least 20% of the subjects from minorities. This will be accomplished by monthly checks on enrollment demographics by REA and discussed at each clinical study meeting to ensure this goal is met.

The REA will pre-screen patients that are scheduled to undergo colonoscopy to identify patients as a potential study participant. Patients scheduled to undergo colonoscopy for suspected colon cancer will be approached by the REA or Physician to ask if they would like to participate in the study and enrolled if they give consent. These informational sources will provide a short description of the study purpose and requirements for participation. Written informed consent will be obtained by the REA from patients agreeing to participate in the study and before commencement of any study activities. Once identified, the REA will screen the patients and obtain consent for study entry. After consent, participating patients will be provided with a study identification number. This number will be utilized on the data collection form, sample labeling and dietary assessments to promote confidentiality throughout the study procedures. At the consent visit, patients will complete a data collection form utilized to confirm study eligibility and record interval history at the sampling time points. Next, they will be given a stool collection kit to take home along with their bowel prep kit, to collect stool prior to bowel prep. If a positive CRC diagnosis is made through the pathology department and confirmed by GI physicians at BSWH facilities, they would continue as a participant in study. This method will allow the collection of stool specimen prior to colonoscopy. **If they are not diagnosed with stage II/III CRC, subjects will be asked if the stool sample can be used in the study as a control. Subjects will be given the option to agree or decline on the prescreening consent form.** [name] will direct the longitudinal specimen collections, assessments and retention. This consent information will be kept at BSWH by either the REA in a password protected file only accessible by the REA or [name]. We plan to recruit 112 stage II/III patients, (110% of what is needed according to power calculations). Recruitment and sample collection will be supported by the clinical practice sites in Temple and Waco, REAs, and facilitated by Principle Investigator [name] PhD, MPH, RD and Physician Drs. [name].

##### **Study procedures:**

This study will collect two sets of data from subjects at baseline (pre-treatment) and on-treatment, as outlined in the Study Design section above.

After specimen collection and coding, microbial DNA will be isolated from the microbiome specimens and fecal metabolites identified. The DNA will be used to conduct DNA sequencing (metagenomics) in accordance with existing protocols through the Integrated Human Microbiome Project (iHMP) study of IBD. The fecal metabolites will be used to produce spectral profiles for quantification using protocols from the iHMP. RNA will be isolated from tissue samples and separate section preserved in Carnoy's to determine biofilm formation. RNA will be used to conduct gene expression assays to confirm taxa identified from sequencing, and blood samples will be used to conduct cytokine assay.

In compliance with BSW protocols, subjects will be screened after consent to verify eligibility. No interventions, device or drugs will be used as part of this observational study. Each participant will serve as his or her own control for the observational (and large cohort) study since this is a prospective cohort design, thus no randomization procedures will be employed. In addition, the questions being asked (e.g. whether the stool microbiome is predictive of treatment toxicity) are dependent upon the participant's baseline data.

This study will consist of potentially five study visits as described below.

**The first study visit** (2 hours) will occur at the BSWH center at which they were initially given the diagnosis of CRC. This visit will occur after consent (after colonoscopy and stool collection at baseline) and screening has occurred and prior to surgery or anti-cancer treatment is initiated. For stool samples, subjects will be given a bag with collection devices, a **Stool Collection History Form**, and instructions (**Comprehensive Stool Kit FED EX Ready**) for collecting stool and contacting the REA for stool drop off or pick up (**instruction for Retraining Your Specimen Samples**). The patients will also be provided with a mailer box if they would rather mail in their specimen, which is stable on ice packs (provided with stool kit) for 24 hours. Prior to Visit 2, patients will complete 2 online dietary assessment tools, the food frequency questionnaire called the **DHQIII (an online survey that takes 30-60 minutes)** and **24-hour recall called the ASA24 (an online survey that takes 20-30 minutes)**, at home prior to their outpatient visit (after surgery) and prior to the beginning of treatment. If the participant needs assistance with either of these surveys, the REA will guide the patient through the online assessment from their computer. This dietary assessment tool is well validated and has been used in numerous large population studies for collection dietary pattern information. Participants will also complete a medical history questionnaire (**COLON-MD Questionnaire 2020-2023**) in an interview with one of the BSW REAs at the time of their first visit.

On the day of surgery, blood will be collected as part of SOC. During surgery, tissue will also be collected from resection, tumor and non-tumor adjacent (2 of each; one for frozen and one for fixation).

**The second study visit** (1 hour) will take place approximately three to four weeks (weeks 3 or 4) after surgery in the outpatient clinic. During this study visit, an additional 2 vials of blood will be taken at the same time as part of the routine clinical visit, and the patient will be given another stool sample kit to take home to collect stool and instructions. The patient will again be asked to take the 24-hour recall online (**ASA24**) complete it at home online within 72 hours of producing the stool sample, and complete the **Stool Collection Form**.

**The third through fifth study visits** (1 hour each) will take place on the 2nd(TD 15), 6th (TD 71) and 10th (TD 128) rounds of IV chemo of treatment (i.e. chemotherapy) at the BSWH center at which they are having their treatment. During this study visit, 2 blood vial samples will be taken as part of the routine clinical visit and the patient will be given two additional stool sample kits to take home to collect stool on the day before chemo starts and before chemo begins and the 2nd day and after their chemotherapy round is complete (i.e. if the infusion starts on Monday, the subject collect a stool sample on that Friday). After

each study visit, the patient will produce 2 stool samples (day before chemo starts and on the 2nd day after their chemo round ends) and drop it off at their treatment hospital or mail (FedEx) it into to the sequencing center at Baylor University. Again, they will be asked to complete the online 24 hour dietary recall (**ASA24**) at home within 72 hours of producing the stool samples. This is the same procedure that will be followed in the fourth and fifth study visits. During each of these visits, the REA or GI physician will ask about incidence and severity of chemotherapy induced diarrhea (**CTCAE – Gastrointestinal/Diarrhea, Grade 1-5**).

The REA will either call the subject or send a text message (if subject agrees) through Twillo after each visit to remind the subject of the days that stool collection and 24 hour (ASA24) recalls should occur.

The REA will obtain interval information from the participant according to the protocol and will provide subjects with stipends for each stool collection provided, which will include \$20 for each specimen collected (stool) up to \$160. If the patient was unable to provide a stool sample at the designated time point due to treatment side-effects they will still be given the compensation for completing the study. Thus, if patients complete all sample collections and all follow up visits, they may receive up to \$160.

Only [name] and the REA will have access to the data-collection sheets and registration forms that will be kept in a locked cabinet at the clinical site.

**Primary data endpoint:** At the end of the observational study we will assess incidence, duration and severity of chemotherapy-induced diarrhea.

**Secondary data endpoints:** The secondary outcomes will include other side effects, including oral mucositis and constipation, circulating cytokine levels, fecal/tissue/blood metabolites, nutrient intake, and changes in microbiome from baseline.

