#### *Dietary Analysis:*

Subject will complete dietary assessments within a 24 hour window of time of stool collection for each stool collection timepoint listed in figure 1. Through the National Cancer Institute (NCI) ASA24-2016 web-portal, the project PI's will register the study allowing utilization of the free ASA24-2016 Dietary Recall instrument. Study participants will be instructed to complete the ASA24-2016 within 24 hours of stool collection at each time point. Participants will also be provided instructions for login to the ASA24-2014 using their confidential study ID. Similarly, the PI will register the study for use of the FFQ to allow the online use of the Diet History Questionnaire. The study participants will be instructed to also complete the online DHQIII prior to the first FOLFOX treatment. The ASA24-2016 asks about food consumed within the last 24 hours based on the on USDA's Automated Multiple-Pass Method (AMPM). Participants have approximately five screens to detail their food intake with prompts to remember food in between meals, source of preparation for the food and a question that asks if food intake was reflective of the participants' typical diet. The recall is respondent-driven in that the detailed questions asked are based on a series of linked question pathways. ASA24 also does not collect any identifying data directly from respondents. However, IP address information is accessed for the purpose of routing information between the server and the respondent's computer -- often the IP address is that of the user's Internet Service Provider (ISP). IP addresses are not stored or tracked by ASA24. However, logs of connections are kept for audit trail purposes. This information is not mined in any way but would be available if there were a legal obligation to release it. Similarly, the Food Frequency Questionnaire (FFQ) or DHQIII also is usually self-administered and has recently become available as a web-based tool, specifically for the Diet History Questionnaire (DHQ). The DHQ was developed and validated by the NCI in two separate studies. Recently, DHQ III has a food list that has been updated from DHQ I based on more recent dietary data and consists of 134 food items and 8 dietary supplement questions. This web-based version takes <1 hour to complete and can be analyzed with the Diet\*Calc software developed by the NCI. This version will be completed by study participants at the time point prior to FOLFOX treatment.

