and microbial clusters (community state types) at baseline using Kruskall-Wallis, and for individual taxa using Pairwise Spearman correlations. We will use PERMANOVA for comparing beta-diversity (weighted UniFrac distances) at baseline by levels of macro- and micronutrients. DESeq2, Kruskall-Wallis and Mann-Whitney tests will be conducted to identify significant differences in tissue and stool taxa or microbial clusters according HEI scores at baseline. The Benjamini and Hochberg false discovery rate (FDR) will be used to correct for multiple testing. Taxa or microbial clusters found to be significantly differentially abundant between treatment time points and baseline will be used to conduct 'random forest' modeling, as previously described, to identify dietary factors that best predict changes in these taxa or clusters. Additionally, we will investigate the tissue and stool microbiome-diet relationship using principal components analysis to identify significant trends among the dietary factors using coinertia analysis. To investigate the microbiome-diet relations during treatment, we will use the microbial clusters and calculate the  $\log_2$  fold change in the clusters from baseline. We will then determine how much the clusters change from baseline according to dichotomous values of macronutrients.

**Microbiome-treatment analysis:** To evaluate differential abundance comparing treatment time points to baseline (prior to surgery and post-surgery/pre-treatment), DESeq2 will be used to control operational taxonomic unit (OTU) over-dispersion between replicates; OTUs will be considered significantly differentially abundant between time points if the false discovery rate (FDR) corrected p-value is below 0.1. A change in relative abundance will be defined as a fold change between mean log relative abundance during treatment phase (week 4, 14, 24) and baseline (prior to surgery). Taxa found to be significantly differentially abundant between treatment time points and baseline (FDR corrected p-value  $<0.05$ ) will be put into an adjusted regression model to control for age, education, income level, marital status, and activity level, diet quality (HEI), tumor stage, medical history with p-values corrected for multiple hypothesis testing using FDR adjustment.

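### The first 24-hour diet recall, and the only diet history, may be completed after surgery, yet baseline diet is analysed against pre-colonoscopy stool and resected tissue

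*Protocol*

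**What the plan says.** Two parts of Protocol section 4.3 set the timing of the diet instruments.

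- **Study procedures, first study visit.** Of Visit 1 it says: "This visit will occur after consent (after colonoscopy and stool collection at baseline) and screening has occurred and prior to surgery". The same paragraph says: "Prior to Visit 2, patients will complete 2 online dietary assessment tools". These are the DHQIII and the ASA24, to be done "at home prior to their outpatient visit (after surgery) and prior to the beginning of treatment". Visit 2 "will take place approximately three to four weeks (weeks 3 or 4) after surgery in the outpatient clinic". For Visit 2 the text adds: "The patient will again be asked to take the 24-hour recall online". The recall due before Visit 2 is therefore the first one.
- **Data Collection, Dietary Analysis.** The general rule is: "Subject will complete dietary assessments within a 24 hour window of time of stool collection for each stool collection timepoint". The ASA24 is then tied specifically to within 24 hours of each stool. For the DHQIII the text says: "This version will be completed by study participants at the time point prior to FOLFOX treatment".

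The specimens have fixed times. The first stool is collected before bowel preparation and colonoscopy, and tumour and adjacent tissue are taken at resection.

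Section 4.4 (Microbiome-Diet Analysis) uses ASA24 and DHQIII data, including the Healthy Eating Index (HEI), to study the effect of diet on the stool and tissue microbiome. Among other tests, it looks for "significant differences in tissue and stool taxa or microbial clusters according HEI scores at baseline".

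**The concern.** A diet measure used as an exposure should describe intake before the specimen it is meant to explain. The visit text does not secure this. It gives no earliest date and does not require completion before surgery, so a patient who does both surveys shortly before Visit 2 is fully compliant. That patient's first recall describes eating during recovery from bowel resection, and would be set against stool and tissue taken weeks earlier. Another patient may complete the same surveys before surgery. Both records would enter the analysis as baseline diet.

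At stake is the diet-microbiome analysis of the first stool and the tissue. The order of exposure and outcome can be reversed, surgery can itself have changed the exposure, and the error differs between patients. An analysis plan cannot repair this later, because a 24-hour recall not taken before surgery cannot be recovered.

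**Working it through.** The plan gives no figure to reproduce. The check sets the timings side by side.

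1. **Specimens.** First stool: before bowel preparation and colonoscopy. Tissue: day of surgery. Second stool: around Visit 2, after surgery and before FOLFOX.

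2. **First ASA24 under the visit text.** It is described under Visit 1, which already follows colonoscopy and the first stool. The consent visit (Subject recruitment and enrollment) issues a stool kit and a data form, and mentions no diet tool. So even prompt completion comes after the first stool. Against tissue, the recall may fall on either side, since Visit 1 precedes surgery and Visit 2 follows it.

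3. **Post-operative part of the window.** 3 weeks × 7 = 21 days; 4 weeks × 7 = 28 days. The ASA24 covers the last 24 hours, so a recall done more than a day after surgery describes post-operative intake only.

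4. **First ASA24 under the Dietary Analysis text.** Within 24 hours of each stool, which on its face includes the pre-colonoscopy stool. For the same patient, the two texts therefore give different records. The protocol does not say which prevails. They also differ for later recalls: the visit text allows 72 hours from the stool, the Dietary Analysis text 24.

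5. **DHQIII.** It is scheduled once. Both texts allow it after surgery, provided it precedes FOLFOX. Its reference period is not stated, so a range has to be assumed for a questionnaire completed just before Visit 2:
   - 30-day period (assumed): 21/30 = 70% to 28/30 = 93% of the period lies after surgery.
   - 12-month period (assumed): 21/365 = 6% to 28/365 = 8%.

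6. **Which baseline.** Section 4.4 uses the word in two senses. The fold-change definition in Microbiome-treatment analysis is pre-surgery only. The sentence before it, and Community state type modeling, include the post-surgery, pre-treatment sample. Section 4.3 also equates baseline with pre-treatment. A post-operative recall suits the Visit 2 stool under the wider sense. Under neither sense does it suit the tissue or the first stool, and no text says which diet record goes with which specimen.

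**The case against.** The strongest reply is that the Dietary Analysis text already places the ASA24 within 24 hours of every stool, which is the anchor wanted for the first one. It refers to a figure that the text available here does not reproduce, so that schedule could not be checked. What stands is that the recall problem is a conflict between two texts, not a design that plainly measures diet at the wrong time. But the conflict is not resolved anywhere, the 24-hour rule is tied to stool and not to tissue, and the sentences specific to the DHQIII set no pre-surgery limit.

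It is also true that the visit text permits completion before surgery, and that the diet-microbiome correlations are framed as a search for potentially important associations. Both points limit the weight of the concern without removing it.

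A reader might infer more than the protocol supports:

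- **That Aim 2 is undermined.** Section 3 words Aim 2 as diet against incidence and severity of chemotherapy-induced diarrhoea. Both surveys must precede treatment, so diet still precedes that outcome.
- **That the error carries into the adjusted treatment model.** HEI is a covariate there, but the text does not say it is baseline HEI, and the ASA24 is repeated at each treatment visit.
- **That the DHQIII necessarily records a post-operative diet.** Its reference period decides this, and is not given.
- **That all 112 patients are affected, or that associations shrink by a known amount.** The first assumes that everyone completes late; the second needs a correlation between recalls that the protocol does not supply.

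**Conclusion.** The concern holds in a limited form. A patient who follows the visit text can have no diet recall that precedes the pre-colonoscopy stool or the tissue, and the baseline diet variable can combine records from before and after resection. The texts permit this; they do not make it certain, and the number of patients affected cannot be derived from them.

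The conclusion is firmest for the ASA24 and for HEI derived from it, where up to 21-28 days of the window are post-operative. For a DHQIII completed just before Visit 2, the post-operative share could be anywhere from about 6% to 93% under the assumed reference periods. The effect is confined to the diet-microbiome analyses of the first stool and the tissue. It should be corrected, because the correction is small and the lost data cannot be collected afterwards.

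**What to change.** 1. **Reconcile the two texts in section 4.3.** Issue the first ASA24 with the stool kit at the consent visit and tie it to the pre-colonoscopy stool. State one recall window in both places.
2. **Require the DHQIII at or soon after Visit 1 and before surgery**, and state its reference period. It would still be filled in after the first stool, but no post-operative time would enter that period.
3. **Keep the second ASA24 at Visit 2.**
4. **In section 4.4, name the pairs.** The pre-surgery diet records go with the pre-colonoscopy stool and the tissue; the Visit 2 recall goes with the Visit 2 stool.

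No new instrument is needed. The cost is a 20-30 minute recall from some people who consent with suspected cancer and prove not to have stage II/III disease; the protocol does not say how many. Holding the 30-60 minute DHQIII until Visit 1, after diagnosis, limits the extra burden to the recall. One limit remains: the recall tied to the first stool will precede the tissue by the interval from colonoscopy to surgery, which the protocol does not give.

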#### **4.4 Data Analysis.**

Classification of taxa associated with side effects or severity: Recently, in an animal model of colon tumorigenesis (AOM/DSS), investigators used the initial microbial community structure (16s rRNA sequencing) to predict tumor burden after exposure to various antibiotics during colon carcinogenesis. In order to conduct a similar analysis and reduce data dimensionality, we will first perform cluster modeling using Dirichlet multinomial mixtures (Holmes et al. 2012) to identify microbial clusters (community state types). To determine which taxa or taxonomic cluster are the best predictors of treatment side effects (CID, mucositis) and severity (stage 3-4), we will conduct 10-fold cross-validation using the RandomForest package (Version 3.6.4) in R (R-studio, Version 0.98.1091; Boston, MA). Specifically, 5,000 trees will be used and the parameter mtry will be set at 100. The taxa with the highest importance scores will be used for further analysis. This procedure will be tested by splitting the data into test and training sets, then running Random Forest using the same procedure described above on the training dataset and comparing the predictive accuracy of the top taxa (based on importance scores) in the test set. Based on this 10-fold cross-validation, we will be able to calculate sensitivity and specificity. These top taxa will then be used to generate receiver operator curves (ROC) and calculate area under the curve (AUC). Each microbial cluster or taxa will undergo independent logistic regression testing to calculate area under the ROC curve using Stata (v13). The command roccomp will be used to compare statistical difference between AUCs and determine the best combination of taxa for classification of CID or mucositis and for severity.

Microbiome-Diet Analysis: To evaluate the impact of diet on the stool and tissue microbiome, we will use the dietary analysis generated from the ASA24 and DHQIII, which includes the Healthy Eating Index (HEI). Prior to analysis, we will conduct normality testing for each variable using Shapiro-Wilk test. For any variables that do not pass, a logarithm transformation will be performed. In order to identify any potentially important diet or nutrient-microbiome associations, we will conduct correlation analysis between dietary macronutrients (carbohydrates, fats, proteins) or micronutrients (vitamins and minerals)

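### The protocol gives two windows for the 24-hour diet recall, 72 hours and 24 hours from the stool, states no direction, and so allows recalls that hold only intake after the stool

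*Protocol*

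**What the plan says.** Protocol section 4.3, Study procedures, sets the recall window in the visit descriptions. At Visit 2 the patient is to "complete it at home online within 72 hours of producing the stool sample". At Visits 3 to 5 the recall is again to be done "at home within 72 hours of producing the stool samples". Each of those three visits has two stools, placed at "day before chemo starts and on the 2 nd day after their chemo round ends".

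The Dietary Analysis section under Data Collection sets a different window, and does so twice: "Subject will complete dietary assessments within a 24 hour window of time of stool collection for each stool collection timepoint", and then "Study participants will be instructed to complete the ASA24-2016 within 24 hours of stool collection at each time point". It also gives the look-back of the instrument: "The ASA24-2016 asks about food consumed within the last 24 hours".

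Section 4.4 says how the data will be used: "To evaluate the impact of diet on the stool and tissue microbiome, we will use the dietary analysis generated from the ASA24 and DHQIII". For the treatment period it plans log2 fold changes in microbial clusters, and adds: "We will then determine how much the clusters change from baseline according to dichotomous values of macronutrients". It also plans random forests to find the dietary factors that best predict taxa or clusters that change during treatment.

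**The concern.** The same instrument at the same visits has two time limits that differ threefold. Study staff and patients would have to choose between them, and different staff could choose differently.

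The longer limit also sits badly with a 24-hour look-back. If the recall is done well after the stool, the recorded food was eaten after the sample and cannot have shaped it. The microbiome-diet analysis treats diet as acting on the stool microbiome, so such a pair puts the exposure after the outcome. Around an infusion there is a second difficulty: a recall attached to the pre-chemotherapy stool may describe eating after chemotherapy began, which blurs the contrast that the paired stools are meant to give.

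This is an instruction at data collection. Only the protocol was available for this review. A SAP could set rules for excluding mistimed pairs, but it could not recover intake that was never recalled.

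**Working it through.** No sample size, power or error rate is involved. The check is interval arithmetic on the stated windows.

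**Inputs**
- Window in the visit text (section 4.3, Visits 2 to 5): 72 hours.
- Window in the Dietary Analysis section (stated twice): 24 hours.
- Look-back of the ASA24 (Dietary Analysis section): 24 hours.
- Stools with a recall under the 72-hour text: 1 at Visit 2 plus 2 at each of Visits 3, 4 and 5, so 1 + 3 × 2 = 7 per patient at most.

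**Formula.** Let t be the hours from stool to recall, positive if the recall is later. The recall covers t − 24 to t hours relative to the stool. For t ≥ 0, the share of the recalled day that lies before the stool is max(0, 24 − t)/24.

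| Recall at t (h after stool) | Period covered (h) | Share before the stool |
|---|---|---|
| 0 | −24 to 0 | 100% |
| 6 | −18 to +6 | 75% |
| 12 | −12 to +12 | 50% |
| 24 | 0 to +24 | 0% |
| 36 | +12 to +36 | 0% |
| 48 | +24 to +48 | 0% |
| 72 | +48 to +72 | 0% |

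**Part of the permitted time with no pre-stool intake.** Under the 72-hour text, read as after the stool: (72 − 24)/72 = 48/72 = 67%.

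**Average pre-stool share.** The documents give no distribution of recall times. If times were uniform after the stool (an assumption), the pre-stool share integrated over the first 24 hours equals 12 hours. The average is then 12/24 = 50% under the 24-hour limit and 12/72 = 17% under the 72-hour limit. Adopting 24 hours everywhere therefore lessens the problem without removing it; a recall at exactly 24 hours still holds nothing from before the stool.

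**Direction.** If the recall came before the stool, all recalled intake would precede it. A recall 72 hours earlier would cover −96 to −72 hours. The wording permits this too.

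**Chemotherapy pair.** The visit text uses a Monday infusion with the second stool on Friday, which puts the first stool on Sunday. A recall 72 hours after the Sunday stool falls on Wednesday and covers Tuesday to Wednesday, after the infusion began.

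**The case against.** The strongest reply accepts the contradiction and disputes what follows from it.

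- **Direction is not stated.** Both windows are given relative to the stool, without before or after. After is the more natural reading of the visit text, but it is a reading. This stands, and the missing direction is itself part of what needs fixing.
- **Aim 2 does not rest on the pairing.** A reader might infer that Aim 2 and every diet-microbiome analysis are compromised. The document does not support that. Aim 2 (section 3) relates dietary history or intake during treatment to diarrhea, and a recall a day or two after a stool is still intake during treatment. Most of the listed diet-microbiome tests are at baseline and can also draw on the DHQIII, which this window does not touch.
- **There is some mitigation.** The REA is to remind patients of the days for stools and recalls, an additional ASA24 is planned before the Visit 2 appointment, and the recall asks whether intake was typical. These help, but none settles which window the reminder should follow, and none requires the recalled day to precede the stool.
- **The last 24 hours may not be the only relevant exposure.** Stool timing itself may slip by up to 72 hours for constipation or diarrhea (section 4.1). This is fair: intake shortly after a stool may still say something about usual diet. It argues for keeping late recalls in a sensitivity analysis, but does not justify two conflicting instructions.

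**Conclusion.** The contradiction is certain on the text: 72 hours in the visit descriptions against 24 hours, stated twice, in the Dietary Analysis section, with no reconciliation and no stated direction. On the natural reading of after, 48 of the 72 permitted hours (67%) give a recall with no intake from before the stool, for up to 7 stools per patient.

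The consequence is limited. It bears mainly on the on-treatment analyses in section 4.4 (cluster change by macronutrient level, and the random forest on dietary factors) and on any baseline use of the ASA24. The DHQIII, the diarrhea endpoint and the power table are unaffected.

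A reader might also infer a definite loss of association strength, or an established reversal of cause and effect. Neither can be drawn from the document. It does not say when recalls will actually be done or how much a late recall still reveals about earlier intake. The 50% and 17% averages rest on an assumed uniform timing and describe overlap in time, not bias in an estimate. The change should be made because it is cheap now and cannot be made after the data are collected.

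**What to change.** State one rule in the Visit 2 text, the text for Visits 3 to 5 and the Dietary Analysis section: the ASA24 is completed on the day of stool collection so that it covers the 24 hours before the stool. Because the pre-stool share falls as the recall is delayed (75% at 6 hours, 50% at 12), ask for it as close to the collection as practicable. Time the planned REA reminder to match.

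Record the date and time of both the stool and the recall. Leave recalls whose 24-hour window starts at or after the stool out of the main stool-paired diet analysis. Keep them in a sensitivity analysis and in the diet-diarrhea analysis.

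The cost is revised instructions, a retimed reminder and two recorded times. The downside is that some recalls drop out of the paired analysis. The number should be small if the new instruction is followed, but could be large if recalls continue to spread over 72 hours.
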